- 2) Overdose Risk Assessment: This assessment is used to determine the potential for future overdose based on prior overdose history, current drug use practices and social context for current drug use. This assessment is not standardized but is compiled from individual items of known risk factors for overdose.
- 3) World Health Organization Quality of Life (WHOQOL-BREF). This is a short assessment to measure general health and physical, social and emotional functioning.
- 4) World Health Organization Alcohol, Smoking and Substance Involvement Screening Test (WHO-ASSIST v.3). This is a multi-item tool to determine areas of substance use and misuse. This assessment battery screens for recent and lifetime use of a variety of substances, including illicit drugs, alcohol, pharmaceuticals and tobacco products.
- 5) Age of First Use: Subjects are asked to provide the ages they first used a variety of substances.
- 6) HIV Risk Assessment Battery: This assessment is used to determine the potential for contracting HIV, hepatitis and other blood-borne illnesses based on drug use and sexual use behaviors.
- 7) Overdose History: This assessment will collect information related to any prior overdose that the subject has experienced or witnessed.
- 8) EQ-5D-3L: This validated quality of life measure asks about problems in mobility, self-care, usual activities, pain and discomfort, anxiety and depression and overall health.

Locator information:

Subjects will be asked to provide a number of sources to ensure they can be contacted for 3, 6 and 12 month follow-up visits. However, because we anticipate a number of high risk subjects to be indigent, subjects may be enrolled if they provide at least one primary source of locator information.

Randomization

Subjects will be randomized to receive either standard of care or the study intervention. We will recruit equal numbers of subjects in the intervention and control arms of the study, meeting eligibility criteria as heroin user or primarily pharmaceutical opioid users.

Follow-up Visits

Follow-up visits will occur at 3, 6 and 12-month after enrollment. All interviews will be by phone. Most assessments given at the baseline interview will be repeated at each follow-up

point. In addition to the assessments subjects will be asked questions about whether they have naloxone and, if not, what happened to any naloxone that was given to them.

Secondary Data Sources

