The study was powered to address aim 1, the impact of the intervention on non-fatal overdose. For the study of each opioid user type (heroin and pharmaceutical opioids) the number of subjects needed in each arm of the study (intervention and comparison) to achieve power of 0.80 to detect a decline in the overdose rate from 20% to 10% at a confidence level of 0.05, is 219 subjects. To increase power somewhat and account for potential loss to follow up, we plan to enroll more subjects, 250 in each arm of each study, for a total of 500 heroin using subjects and 500 pharmaceutical opioid, non-heroin using subjects. Other outcomes to be analyzed include drug use and services utilization. Data on brief interventions in ED's shows declines in drug use and ED utilization of at least 40%. Specifically in Washington State, the Screening and Brief Intervention Referral and Treatment (SBIRT) found a 45% reduction in average days of drug use among high risk heroin users who received a brief intervention in an ED (from 15.8 days to 8.7 days in the prior month) and 41% reduction among high risk pharmaceutical opioid users (12.8 to 7.5 days).

Assumptions behind the power estimate are based upon an annual rate of non-fatal heroin overdose estimated to be a median of 25% across studies and for fatal overdoses approximately 1%. For the purposes of this sample size estimate we are conservatively assuming a total annual overdose rate for heroin users of 20%. We believe that a reduction of the OD rate by 50% may be possible based on the potential for additive effects of the OOPEN and the BBCC interventions. Preliminary data on overdose rates for pharmaceutical opioid

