Aim 1 Test whether the intervention group has lower rates of opioid overdose and longer time to occurrence of overdose. Overdose will be ascertained at 12 months via self-report and across at least 24 months via administrative data. Because randomized controlled studies are designed to account for potential confounding factors by distributing confounders, measured and unmeasured, equally across comparison and intervention groups, the initial unadjusted analysis will be a logistic regression analysis comparing the probability of opioid overdose in the two study arms. To examine differences in the time to overdose and to account for time varying covariates, such as overdose risk factors, survival analyses will be conducted with the outcome time to overdose(s). A Cox proportional hazards model will be used to investigate the possible association between these factors and event time. We will use sandwich standard error estimates in all statistical tests. Multivariable logistic regression analyses will be conducted to examine the association between predictors and moderators and of the odds of overdose occurrence. Predictors will include treatment assignment and overdose risk factors such as concomitant drug use, interruption in tolerance and homelessness. Potential effect modification will be assessed by including interaction terms for the treatment assignment by severity of opioid and other substance use as measured by the ASSIST. For the pharmaceutical opioid only group, effect modification by opioid user type will be assessed; opioid user typologies will be based upon which inclusion criteria subjects met.

Aim 2 Test whether the intervention group has fewer overdose risk behaviors. These are measured as both binary and continuous data. Binary data will be examined with logistic

regression and continuous data analyzed with ordinary least-squares regression. Analyses will adjust for the overdose risk behavior level or frequency reported at baseline as a concomitant variable, the outcome is the overdose risk behavior at 12 months, and the primary predictor is the treatment group assignment. We will compute robust standard error estimates for each model and use them in all hypothesis tests and confidence intervals.

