In order to determine whether there is recruitment reactivity, whether those enrolled in either arm of the study have a change in behaviors compared to those not enrolled, we will examine ED re-visit rates at two years for those receiving standard care compared to those with similar demographic characteristics, CPT codes and ED visit dates, but were not enrolled. While this will not directly measure the impact of recruitment on overdose, it will provide some information about recruitment reactivity. Subsequent to intent to treat analyses we will examine whether any subjects in the standard care group received take-home naloxone and overdose prevention and intervention training i.e. “crossed over”. If so, it is possible that this intermediate group might be more similar to the intervention than the standard care group. Crossovers will be identified by an interview question, such as “Did you possess or have ready access to naloxone during the past 3/6 months?” If there is a group that crossed over, post-hoc analyses will compare overdose rates at two years for the cross over group compared to each of the other two study arms. Completion level of administrative data will be assessed by the interview questions at each follow up that document what types of services, in broad categories, were

obtained at non-HMC or non-UWMC facilities or ambulance services not in Seattle-King County. This will allow for an evaluation of *ascertainment bias*, that is, how complete data based on HMC/UWMC and King County ambulance data are and whether there are differential levels of data completion by study arm assignment.

Missing data and dropouts

Missing data will be minimized by the study procedures described above. However, missing data are inevitable and could lead to biased results. Baseline data values and study arm assignment will be examined to determine the relationship with missingness. Sensitivity analyses will be conducted that assume any person lost to follow up had constant levels of drug use based upon their most recent measurement point. This will provide some guidance as to the amount of bias possibly introduced by missing data.

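### The one stated assumption for missing drug-use data, that lost subjects stay at their last level, is an unreliable gauge of missing-data bias for Aim 2

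*Combined protocol and SAP*

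**What the plan says.** The section Missing data and dropouts contains two steps. The first is descriptive: "Baseline data values and study arm assignment will be examined to determine the relationship with missingness". The second is the sensitivity analysis: "Sensitivity analyses will be conducted that assume any person lost to follow up had constant levels of drug use based upon their most recent measurement". Its purpose is then given: "This will provide some guidance as to the amount of bias possibly introduced by missing data".

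The outcome concerned belongs to Aim 2, which the Objectives list as a primary aim. Under Planned analyses, Aim 2, "the outcome is the overdose risk behavior at 12 months", and the model is baseline-adjusted: "Analyses will adjust for the overdose risk behavior level or frequency reported at baseline as a concomitant variable". No method for missing outcomes is named there, which implies an analysis of observed cases. On timing, "Follow-up visits will occur at 3, 6 and 12-month after enrollment", so the most recent measurement of a lost subject can be baseline, 3 months or 6 months.

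Nothing elsewhere supplements this. The generalized linear model check under Aims 3 and 4 concerns the form of the cost model. The ascertainment check under Other analyses concerns completeness of administrative records.

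**The concern.** The gap between the main result and this sensitivity result will be read as a measure of missing-data bias. It measures something narrower: how the arm difference would look if no lost subject changed after last contact, with the same rule in both arms. Two failures follow.

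- **False alarm.** A subject lost before the 3-month call is held at the enrolment value. If use generally falls after enrolment and the arms lose different proportions early, the rule creates an arm difference. With equal early loss it shrinks a real effect.
- **False reassurance.** If subjects improve, are interviewed, and then relapse and disappear, the value carried forward is the good one. The sensitivity result then agrees with the observed-case result although both are wrong.

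The protocol makes appreciable loss plausible. It expects indigent subjects, allows enrolment with one locator source, conducts follow-up by telephone and bars contact during incarceration. What is at stake is whether a reader can judge the robustness of a primary aim.

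**Working it through.** **Inputs from the protocol (Sample Size Calculation).** 250 subjects per arm for each user type. Days of use in the prior month fell from 15.8 to 8.7 for heroin users (7.1 days; 7.1/15.8 = 45%, as stated) and from 12.8 to 7.5 for pharmaceutical opioid users (5.3 days; 5.3/12.8 = 41%, as stated). These are pre-post changes in another programme.

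**The plan's own figure.** 219 per arm (20% versus 10%, power 0.80, alpha 0.05) reproduces with a two-sided, continuity-corrected formula; without the correction it is 199. No dropout rate is given. Going from 219 to 250 leaves room for 1 − 219/250 = 12.4%.

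**Assumptions.** Dropout rates, timing and mechanism, SD 10 days, correlation 0.4 between measurements, and a fall under standard care. None is in the documents. SD and correlation affect only the rejection rates, not the mean shifts.

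**1. No treatment effect, unequal early dropout.** Both arms fall by F. Dropout is random, at d_I and d_C, and a share e of losses comes before the first call. Observed cases have expected difference 0. Carrying forward gives

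shift = (d_I − d_C) × e × F

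| d_C vs d_I | e | F (days) | Shift (days) | Rejection at 250 per arm |
|---|---|---|---|---|
| 15% vs 25% | 1 | 7.1 | 0.71 | about 13-14% |
| 15% vs 25% | 1 | 5.3 | 0.53 | about 10% |
| 15% vs 25% | 0.5 | 7.1 | 0.36 | about 7-8% |
| 15% vs 25% | 1 | 3.5 | 0.35 | about 7-8% |
| 15% vs 20% | 1 | 7.1 | 0.36 | about 7-8% |
| equal | any | any | 0 | no inflation |

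Rejection rates come from simulating the Aim 2 model (least squares on arm and baseline, robust standard errors). They move by a point or two with the correlation structure. Observed cases reject in about 4-6%.

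**2. True effect, equal early dropout.** With random early loss d in each arm, the carried-forward effect is (1 − d) × true effect. For a 3-day effect and d = 25%, this is 0.75 × 3 = 2.25 days (about 2.2 in simulation). Observed cases give about 3.

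**3. Relapse after last contact.** No arm difference otherwise, and 20% lost per arm after a follow-up interview. The lost intervention subjects then relapse by 7.1 days. True difference = 0.20 × 7.1 = 1.42 days in favour of standard care. Observed cases give about 0, and carrying forward gives about 0. The gap between the two analyses is 0, while the bias is 1.4 days.

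**The case against.** Several objections have force, and most limit the point without removing it.

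- **The plan is modest.** It promises only some guidance, and holding use constant is right if use really stays flat. That stands. But the guidance is about the amount of bias, and cases 1 and 3 show that the gap need not track it.
- **A reader might infer that the plan's own figures contradict the constant-level rule.** They do not. The programme "found a 45% reduction in average days of drug use among high risk heroin users who received a brief intervention in an ED". Those are treated people in another setting, and the figures describe neither dropouts nor standard care. A fall in both arms here is an assumption.
- **A reader might infer that the trial's error rate is inflated.** It is not. Rejection above 5% belongs to the sensitivity check. In case 1 the observed-case analysis is unbiased.
- **A reader might quote larger rates at 500 per arm.** The 7.1-day fall is for heroin users, who number 250 per arm. Pooling both user types means an average fall of (7.1 + 5.3)/2 = 6.2 days, with about 18-20% rejection at 15% versus 25% early dropout.
- **The planned look at missingness by arm would reveal unequal dropout.** True. It would warn of the condition behind case 1, but it does not bound bias and does not help in cases 2 and 3.
- **Case 3 is not peculiar to carrying values forward.** Multiple imputation without a shift would also return about 0. This is correct, and it is why the shift is the essential part of the remedy.
- **Days in the prior month is not the listed outcome.** The data schedule lists frequency of use over three or six months, and Aim 2 includes binary measures. The figures in days are therefore illustrative, and the remedy must work on each outcome's own scale.

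**Conclusion.** The point holds as a worthwhile, inexpensive improvement. The one stated assumption is an unreliable gauge of missing-data bias. Depending on unstated dropout rates and timing, it can show a false difference of roughly 0.35 to 0.7 days, reduce a true 3-day effect to about 2.2, or show nothing when the bias is about 1.4 days. The false difference requires a post-enrolment fall in both arms and unequal early loss. The shrinkage requires early loss and a true effect. The missed bias requires relapse after the last interview. The documents establish none of these conditions, and they do not rule them out. They do not support the conclusion that the main Aim 2 estimate is biased, or that the constant-level assumption is known to be false in this population.

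**What to change.** In Missing data and dropouts, make the following the main sensitivity analysis:

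1. Impute missing 12-month Aim 2 outcomes by multiple imputation, separately within each arm, from baseline, 3-month and 6-month values.
2. Add a shift to the imputed values in the intervention arm only, in the standard care arm only, and in both. Use the outcome's own scale for continuous measures and the log-odds scale for binary measures. Set the range in advance for the 12-month measure, whose recall window is six months where the earlier interviews use three.
3. Report the shift at which the Aim 2 conclusion changes, so that readers can judge whether it is plausible.

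Keep the constant-level analysis as one labelled scenario, and no longer present it as the gauge of bias.

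The change is a few sentences and some extra programming. It needs no new data or subjects. The downside is small: the reader gets a range of results rather than one number.

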- Subjects will be given a study brochure that covers the information in the video and reviews the Washington State 911 Good Samaritan overdose law which provides immunity from prosecution for drug possession charges to overdose victims and bystanders who seek aid in an overdose event.
- Prescribing and dispensing overdose rescue kits including 2 doses of intra-nasal naloxone, a disposable rescue breathing mask, and disposable gloves.
- Subjects in the intervention group will be informed that they may have one replacement of the naloxone kit (2 doses) during the 12 month study period.

We expect the intervention to take 30-45 minutes on average based on our experience and that this is feasible and reasonable for subjects and interventionists.

Fidelity assessment for the BBCC will be done with the shortened Motivational Interviewing Treatment Integrity (MITI) instrument.

Schedule of and Sources Data Obtainment

MEASURES	DATA SOURCES AND TIMING					
	Interview			Administrative		
	Case Report Form	Base-line	3 & 6 mos.	12 mo.	Up to 10 yrs.	Up to 10 yrs.
PRIMARY AIMS						
Aim 1: Overdose						
Subject overdosed prior 3/6* months	X		X			
Subject overdosed Y/N & Date						X
Aim 2: Drug use and other overdose risk behaviors						
Alcohol/Drugs 3/6 month use frequency	X		X		X	
Opioid use following interruption past 3/6 months	X		X		X	
Using opioids without others present	X		X		X	
Avg. daily opioid dose- Prescribed Opioid Users	X		X		X	
Opioid substitution drug treatment prior 3/6	X		X		X	
Other drug treatment sought or used prior 3/6	X		X		X	
SECONDARY AIMS						
Aim 3: Health care utilization						

ED, Outpatient, Inpatient and Ambulance- # & Aim 4: Health care costs Hospital-based total direct health care costs			x	x
Aim 5: HIV Risk Behaviors	x	x	x	x
CO-VARIATES & POTENTIAL EFFECT MODIFIERS				
Demographics	x			
Employment, health insurance, income, housing	x	x	x	
Alcohol/Drugs ages of first use	x			
Medical status and satisfaction (WHO QOL BREF, EQ-5D- 3L)	x	x	x	
Behavior change plans and readiness	x			
Overdose lifetime history	x			
Possessed, "carried" naloxone, # of days past 3/6	x	x	x	
Overdose # witnessed events past 3/6 months	x	x	x	
Source of naloxone- Study, other	x	x	x	
Subject had naloxone administered to them, #, by Disposition of naloxone	x	x	x	x
Subject had negative/allergic reaction to naloxone	x	x	x	
FIDELITY ASSESSMENT OF BASELINE				
Overdose prevention & intervention training. Item Motivational Interviewing Treatment Integrity 3.1.1	x			

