*Past 3 months timeline for 3 and 6 month follow ups, past 6 months used at 12 month follow up.

Brief Behavioral Change Counseling (BBCC)

The BBCC will be conducted according to the demeanor and guidelines of Motivational Interviewing (MI), a style for counseling patients about sensitive behaviors and for giving them information to enhance their health and safety in a non-judgmental manner. MI has been widely implemented in brief intervention studies for drug use and other behavior change. MI is non-confrontational and respectful of subjects' autonomy to discuss or not discuss sensitive topics. The BBCC will consist of 4 elements:

- 1) The interventionist will show to the patient an approximately 8-minute video on overdose prevention, recognition and intervention, which subjects will view on a laptop while they are using headphones. The interventionist will debrief the video with subjects and answer questions.
- 2) Next, the interventionist will review with subjects their overdose risk. This task involves informing subjects of the “good news” about overdose risks they are NOT incurring in their current behaviors for the purpose of reinforcing and hopefully continuing more positive health behaviors (e.g., not inappropriately mixing other drugs or alcohol with

opiates). Next, the interventionist will respectfully and in a neutral tone review with subjects the behaviors that currently place them at risk for opiate overdose (e.g., using opiates when alone or after a long period of abstinence).

- 3) From the video and risk feedback, the interventionist will segue into an open discussion of any changes subjects are thinking of making to increase their safety from overdosing. If at any time during the interview, subjects indicate that they would prefer to quit opiates or to seek opiate detox or treatment, the interventionist will help with these referrals. The discussion will culminate in a summary of healthy changes, if any, that subjects intend to make. Subjects will take with them a handout that has been customized to summarize any changes subjects indicate that they want to make.

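### The only planned missing-data sensitivity analysis carries the last drug-use value forward: a weak check on the 12-month Aim 2 outcome, with no counterpart for missing self-reported overdose

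*Combined protocol and SAP*

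**What the plan says.** Missing data and dropouts contains two analytic steps. The first is descriptive: "Baseline data values and study arm assignment will be examined to determine the relationship with missingness". No adjustment or imputation follows from it. The second is the sensitivity analysis, which will "assume any person lost to follow up had constant levels of drug use based upon their most recent measurement point". In substance this is last observation carried forward, or baseline carried forward for someone who completes no follow-up interview. Its stated purpose is modest: "This will provide some guidance as to the amount of bias possibly introduced by missing data". The section does not say how missing 12-month values are handled in the primary analysis.

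Planned analyses, Aim 2, fixes the time point: "the outcome is the overdose risk behavior at 12 months, and the primary predictor is the treatment group assignment". On the type of outcome it says: "These are measured as both binary and continuous data. Binary data will be examined with logistic" regression, with least squares for the continuous ones.

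In the table under Schedule of and Sources Data Obtainment, the drug-use measure is "Alcohol/Drugs 3/6 month use frequency", and the footnote gives the recall windows: "Past 3 months timeline for 3 and 6 month follow ups, past 6 months used at 12 month follow up". The baseline window is not in that footnote.

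Sample Size Calculation cites an outside state programme in which heroin users who received a brief intervention went "from 15.8 days to 8.7 days in the prior month".

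**The concern.** A sensitivity analysis for missing data should show what happens to the conclusion if those lost differ from those retained. This one tests a single, specific belief, that use stops changing on the day of last contact, and that belief does not suit this trial well. The intervention is meant to change use, and the programme figures the plan cites show use falling. Participants may enrol with one contact source (Locator information) and are not contacted while in jail (Secondary Data Sources), so loss may well be related to use.

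Three weaknesses follow:

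- The no-change assumption can push the estimate up or down, so the check is not reliably conservative.
- The values carried forward come from 3-month recall at the 3- and 6-month interviews, while the outcome uses 6-month recall. The plan does not say whether they are rescaled.
- A single filled-in value is analysed as if observed, so the standard error omits the uncertainty of imputation. The robust standard errors planned for Aim 2 do not restore it.

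The assumption also concerns drug use only. The trial is powered on overdose, and missing overdose interviews have no comparable check. A missed 3-month interview leaves months 0 to 3 outside every later recall window.

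At stake is the reassurance readers would draw if the carried-forward result agrees with the primary one, or the doubt they would draw if it does not.

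**Working it through.** **Inputs from the documents.** 15.8 and 8.7 days in the prior month; 219 needed and 250 enrolled per arm (all Sample Size Calculation); recall of 3, 3 and 6 months at the three interviews.

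**The plan's own figures.** (15.8 − 8.7)/15.8 = 45%, as stated. The 219 per arm is reproduced for 20% vs 10% with a two-sided 0.05 test, power 0.80 and continuity correction. It matters here only because 1 − 219/250 = 12.4% is the loss that would bring 250 down to 219. It is a margin, not a predicted loss rate; the documents predict none.

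**1. No true effect, both arms improve.** Assume that both arms fall from 15.8 to 12 days, that those lost improve like those retained, and that all loss comes straight after baseline. With loss *d*, the carried-forward arm mean is (1 − *d*) × 12 + *d* × 15.8, so the false difference is (difference in loss) × 3.8.

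| Loss, control vs intervention | Control mean | Intervention mean | False benefit |
|---|---|---|---|
| equal | same | same | 0 |
| 15% vs 10% | 12.57 | 12.38 | 0.19 day |
| 30% vs 15% | 13.14 | 12.57 | 0.57 day |

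Swapping the loss rates turns the false benefit into a false harm of the same size. Loss after the 3- or 6-month interview would shrink these figures, because some of the fall would already be recorded.

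**2. A true effect, change after loss.** For illustration, take controls at 15.8 and retained intervention participants at 8.7, a difference of 7.1 days.

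- Intervention participants lost after baseline who respond like those retained: truth 7.1, carried-forward estimate 7.1 × (1 − *d*). This is 6.22 at 12.4% loss and 4.97 at 30%, too small by the loss rate.
- Intervention participants last seen at 8.7 who then return to 15.8: truth 7.1 × (1 − *d*), carried-forward estimate 7.1. At 12.4% loss, 7.1/6.22 overstates the effect by 14%; at 30%, 7.1/4.97 overstates it by 43%.

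So with unchanged controls the error can go either way, whether or not loss differs by arm.

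**3. Recall window.** Take a yes/no item on any occurrence in the window, with 20% prevalence over 3 months.

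- Two 3-month windows independent within a person: 1 − (1 − 0.20)² = 36% over 6 months, a gap of 16 points.
- Full persistence (the same people in both windows): 20% over 6 months, a gap of 0.

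The gap applies only to imputed people. At 12.4% imputed, an arm's prevalence is understated by at most 0.124 × 16 = 2.0 points. Between arms, with no true effect, the most it can add is (difference in loss) × 16: 0 with equal loss, 0.8 point at 15% vs 10%, 2.4 points at 30% vs 15%. Here the arm with more loss looks better; in step 1 it looks worse. The two errors need not cancel, and they make the result hard to interpret.

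**The case against.** The strongest reply is that this is only a sensitivity analysis. A reader might infer that carrying values forward biases the Aim 2 result. It does not: that estimate comes from the models in Planned analyses and is untouched. The plan also claims only limited guidance, and its look at missingness by arm and baseline would reveal the unequal loss on which step 1 depends. All of this stands and limits the point to the quality of the check.

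A reader might also infer that nothing is planned for missing overdose. That is too strong. Hospital, ambulance and medical-examiner sources do not need a completed interview, follow-up through administrative data runs to at least 24 months, and Other analyses plans to assess completeness of those data by arm. That assessment addresses ascertainment in the records, however. It does not test assumptions about people whose interviews are missing, so a narrower gap remains.

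On recall, the text speaks of constant levels of use, which could be read as a rate and rescaled. On a rate or days-per-month scale the mismatch largely disappears. The plan does not specify the scale, so this is an ambiguity to close rather than a demonstrated error.

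Finally, the 41–45% falls are before-after figures from an outside programme, in people who received a brief intervention. They are not trial data and say nothing about controls. They make constant use doubtful but do not show how far use will move. The 12-day endpoint and the loss rates in step 1 are assumptions, and 30% is more than twice the 12.4% margin.

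**Conclusion.** The concern holds in a limited form. The single sensitivity assumption is a weak check on the 12-month Aim 2 outcome: it assumes no change after loss, ignores imputation uncertainty and leaves the recall scale undefined. Its own result can be wrong in either direction.

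The sizes are modest and depend on assumptions. The false difference is 0 with equal loss, 0.19 day at 15% vs 10% and 0.57 day at 30% vs 15%, given a shared fall from 15.8 to 12 days and loss straight after baseline. Even 0.57 day is about 8% of the 7.1-day fall cited in the plan. The recall gap is 0 to 16 points per imputed person on an item with 20% three-month prevalence. It would be wrong to read 16 points as bias in a treatment comparison, because it is diluted by the share imputed and vanishes between arms with equal loss and no effect. No number is attached to the understated standard error.

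Missing self-reported overdose lacks a sensitivity analysis, with administrative records as partial cover. The plan should be changed, but the documents do not support a claim that its primary results are biased by this analysis.

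**What to change.** Replace or supplement the carried-forward analysis in Missing data and dropouts as follows.

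- Impute missing 12-month Aim 2 values by multiple imputation, separately by arm, from the baseline, 3- and 6-month values. Put drug use on a common rate scale (such as days per month) or on the 12-month recall scale, and state which. In step 1, where those lost improve like those retained, this would be expected to return 12 days in both arms and so remove the false difference.
- Add a delta-adjusted (tipping-point) version for Aim 2: worsen the imputed intervention values in steps until the conclusion changes, and report the step at which it does. This covers the return-to-baseline case in step 2, which imputation alone does not.
- Apply the same delta-adjusted approach to missing self-reported overdose.
- If the carried-forward analysis is kept, state the scale on which values are carried and describe it as one scenario among several.

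The cost is SAP wording, some extra analysis work and possibly wider intervals. No new data are needed, since all the interview values are already scheduled.
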